8.3 Sample Size and Power Determination

Our study has been powered to allow us to determine non-inferiority of effectiveness both overall and within two of the three skin type strata. Because a clinical question is whether effectiveness is equivalent within each skin type sub-group, our sample size has been determined in order to provide adequate power for these skin type-specific analyses. We have pre-specified two primary effectiveness outcomes and assume a type I error rate for each outcome at the one-sided alpha = 2.5% level which is standard for a non-inferiority trial and analogous to the more familiar two-sided alpha = 0.05. Although this alpha level does not explicitly account for multiple comparisons, we believe that doing so would be unnecessarily conservative as both our patient-reported and physician-reported outcome measures assess the same outcome and are expected to be very highly correlated⁴⁶. Assuming a 50% response rate in both the office based phototherapy group and the home-based group and a non-inferiority margin of 15% (i.e. the 95% two-sided confidence interval on the difference in response rates between office and home-based groups excludes 15%), we calculated that 175 patients of each skin type would need to be included in each study arm to have 80% power to establish non-inferiority of home based phototherapy at a one-sided significance level of 2.5%. In the pooled sample, we will have 99% power for a non-inferiority

margin of 15%. Our non-inferiority margin has been iterated with our patient research partners and expert dermatologists. It is well within previous suggestions of non-inferiority for psoriasis treatments⁴⁷. We also note that the FDA accepts a 15% margin or greater for the study of biosimilars of biologics for moderate to severe psoriasis^{48, 49}. Additionally, our estimates are more conservative (i.e., require a larger sample size) than the non-inferiority margin specified in the pragmatic trial of home versus office based phototherapy conducted in the Netherlands which only required 100 patients per group total³⁰. Our estimates require a larger sample size compared to the Netherlands study primarily because we have set a higher bar for effectiveness. Based on preliminary data, the rate of DLQI ≤5 is anticipated to be similar to the estimate of achieving clear or almost clear skin, providing 80% power for the same non-inferiority margin for this outcome¹⁵.

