Comparator Device	Daavlin 7 series 3 panel narrow band phototherapy home units (have 8-12 bulbs and a smaller, flat surface with door, measuring 21" wide, 74.5" tall, and 23.5"). The unit will have a dosimetery controller, a UV sensor built in that measures the intensity of the light. This unit is a class II device with a FDA 510K indication for psoriasis, vitiligo and atopic dermatitis/eczema.
Duration of administration (if applicable)	Approximately three times per week x 12 weeks

Reference therapy	Office based narrow band phototherapy (units typically have at least 24 bulbs in a surround structure)
Statistical Methodology	 The co-primary endpoints of this study will be: Physician Global Assessment (PGA) score of clear/almost clear (at week 12 or the time of phototherapy discontinuation, whichever comes first) Dermatology Life Quality Index (DLQI) score of ≤5 which corresponds to no to small impact of dermatologic disease on quality of life at week 12 Secondary outcomes include: Physician measured body surface area (BSA) x PGA Concomitant topical psoriasis treatment Patient reported time spent on phototherapy Patient reported time and cost associated with travel for phototherapy treatments Phototherapy number and dose Duration of treatment response during observation period
Safety Evaluations	The primary safety outcome is the proportion of patients reporting treatment- emergent adverse events. Treatment emergent adverse events include patient reported burns and their severity. We will also collect data on all Serious Adverse Events whether treatment related or not.
Data and Safety Monitoring Plan	The local investigators are responsible for monitoring patient safety as per standard of care. Data quality will be monitored by the study Principal Investigator and his team centrally with queries and auditing of sites as necessary.

BACKGROUND AND STUDY RATIONALE

This study will be conducted in full accordance all applicable University of Pennsylvania Research Policies and Procedures and all applicable Federal and state laws and regulations including 45 CFR 46, 21 CFR Parts 50, 54, 56, and Good Clinical Practice: Consolidated Guidelines approved by the International Conference on Harmonisation (ICH).

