3.2 Study Endpoints

3.2.1 Primary Study Endpoints

The first primary effectiveness outcome is treatment response, a dichotomous indicator of whether a patient has achieved clear/almost clear skin (score of 0 or 1), based on the Physician's Global Assessment (PGA) at the earlier of week 12 or discontinuation of phototherapy. See Appendix B for PGA tool.

The second co-primary outcome is the patient-reported Dermatology Life Quality Index (DLQI) at week 12. We will dichotomize DLQI at a score of 0-5 (corresponding to no to small impact on quality of life) versus a score $\ge 6^{44}$.

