We hypothesize that effectiveness of home-based UVB phototherapy will not be inferior to that of officebased phototherapy on either of the two primary effectiveness outcomes. At the conclusion of the trial we will report the response rate, i.e. the proportion of patients achieving clear/almost clear skin on the PGA at the earlier of 12 weeks after initiating home or office-based phototherapy or discontinuation of phototherapy and the proportion of patients with no to small impairment on quality of life (DLQI 0-5) at week 12 for each treatment arm with 95% confidence intervals. These measures will be reported for the complete study cohort and separately for two of the three skin type sub-groups. We will not be able to test the hypothesis of non-inferiority of home vs. office treatment in skin type V/VI. We will accumulate additional data in this group which will improve the precision of our estimates of efficacy in this patient population as well as gather additional data about barriers patients with skin type 5/6 face in accessing home or office base phototherapy that lead to inequities and health disparities in patients with psoriasis.

To account for stratification by skin type, which induces non-independence across strata, pooled analyses will be conducted using logistic regression adjusted for treatment arm and skin type. Skin-type adjusted risk differences between home and office-based phototherapy will be computed from odds ratios using marginal standardization. Statistical inference will be based on adjusted risk differences according to non-inferiority principles. Home-based phototherapy will be determined to be non-inferior relative to office based phototherapy if the lower bound of the adjusted two-sided 95% confidence interval for the risk difference is greater than the pre-specified non-inferiority margin of 15%.

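### PGA and DLQI are called co-primary, but the plan does not say whether one or both must meet the margin, and its correlation argument for leaving alpha unadjusted does not hold the overall error at 2.5%

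*Combined protocol and SAP*

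**What the plan says.** The Study Summary introduces PGA clear or almost clear and DLQI of 5 or less together: "The co-primary endpoints of this study will be". Section 3.2.1 repeats the label: "The second co-primary outcome is the patient-reported Dermatology Life Quality Index (DLQI) at week 12". Section 8.1 hypothesises that home treatment will not be inferior "on either of the two primary effectiveness outcomes", which most naturally means on both. Section 8.4.2 describes the primary efficacy endpoint as both physician-reported and patient-reported.

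The decision rule at the end of section 8.1 is worded differently. It declares home treatment non-inferior from the confidence interval for one risk difference. It does not name the outcome or say how two results are to be combined.

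Section 8.3 sets alpha outcome by outcome: "assume a type I error rate for each outcome at the one-sided alpha = 2.5% level". It then declines to adjust: "Although this alpha level does not explicitly account for multiple comparisons, we believe that doing so would be unnecessarily conservative". The reason is that the two measures "assess the same outcome and are expected to be very highly correlated". No correlation is given. The sample size starts from this premise: "Assuming a 50% response rate in both the office based phototherapy group and the home-based group and a non-inferiority margin of 15" percentage points. It arrives at 175 per arm in each skin type for 80% power. For DLQI the section adds that the expected rate is similar, "providing 80% power for the same non-inferiority margin for this outcome". The plan gives no joint power and no overall error rate.

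**The concern.** The text points two ways on the main claim. The co-primary label, the hypothesis and section 8.4.2 lean towards requiring both outcomes. In that case no multiplicity adjustment is needed, and the correlation argument in section 8.3 has no purpose. That argument is needed only if success on one outcome is enough, and high correlation then reduces the error inflation without removing it.

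Two things are at stake. If PGA meets the margin and DLQI does not, or the reverse, the plan does not say whether home treatment has been shown non-inferior. A rule chosen once results are known would not be credible. Also, the power in section 8.3 is presented as power to establish non-inferiority of home phototherapy, but it was calculated for one outcome. A reader who takes both outcomes to be required would credit the skin-type analyses with more power than they have.

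**Working it through.** **Inputs.** From section 8.3: 50% response in both arms, a 15-point margin, one-sided 2.5% per outcome, and 175 per arm in a skin type. Pooled size: 1050/2 = 525 per arm if recruitment is full (section 4.5). If the strata fill as section 3.1 lists them (350, 350 and about 80), it is 780/2 = 390 per arm. The correlation r between the two test statistics is not in the documents. It is taken over a range, with most weight on 0.9 to 0.95 because the plan expects it to be very high.

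**Step 1: reproduce the plan's figure (one outcome).**
- SE = sqrt(2 × 0.5 × 0.5 / 175) = 0.0535.
- Power = Φ(0.15/0.0535 − 1.96) = Φ(0.846) = 80.1%.
- The same formula gives 98.7% at 390 per arm and 99.8% at 525. The stated 80% and 99% therefore both reproduce, per outcome.

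**Step 2: both outcomes required.** The chance of a false overall claim is at most 2.5%, because any such claim needs a false success on at least one particular outcome tested at 2.5%. Joint power = Φ₂(0.846, 0.846; r), where Φ₂ is the bivariate normal distribution function. At r = 0 this is 0.801² = 0.642.

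**Step 3: one outcome enough, each at 2.5%.** Take the least favourable case, with both outcomes truly at the margin. Error = 2 × 0.025 − Φ₂(−1.96, −1.96; r). At r = 0.9 this is 0.05 − 0.0148 = 0.0352.

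| r | Joint power, 175 per arm | Joint power, pooled 390 / 525 per arm | Error if one is enough |
|---|---|---|---|
| 0 | 64.2% | 97.4% / 99.6% | 4.9% |
| 0.5 | 68.9% | 97.6% / 99.6% | 4.5% |
| 0.9 | 75.1% | 98.1% / 99.7% | 3.5% |
| 0.95 | 76.6% | 98.3% / 99.7% | 3.2% |
| 1 | 80.1% | 98.7% / 99.8% | 2.5% |

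A simulation of correlated binary outcomes with Wald intervals agreed to within about 1.5 points of power and 0.2 points of error.

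**Step 4: how likely is a split result?** If home and office are truly equal, the chance that exactly one outcome meets the margin in a skin type is 2 × (single power − joint power). At r = 0.9 this is 2 × (0.801 − 0.751) = 10%. At r = 0.95 it is 2 × (0.801 − 0.766) = 7%.

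**Is r = 1 plausible?** It is not. One outcome is rated by the clinician and the other by the patient. Under section 3.2.1, PGA may be taken at discontinuation, while DLQI is taken at week 12.

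**The case against.** The strongest reply is that the plan keeps its own promises. Section 8.3 states the 2.5% for each outcome and the DLQI power for that outcome alone, and Step 1 shows that both are delivered. The lack of adjustment is disclosed. A reader might infer that the plan misses its stated error and power under every reading. The documents do not support that, because the plan claims neither a family-wise 2.5% nor a joint 80%. A third reading also fits the text: a separate conclusion for each outcome, with a split result reported as such. This stands. What remains is that section 8.1 draws a conclusion about home phototherapy as a whole and does not say how two results lead to it.

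A reader might also infer that the main analysis is underpowered. It is not: the pooled analysis is primary, and its joint power is 97% or more. The loss falls in the skin-type analyses, which section 8.2 lists as secondary. It still matters, because section 8.3 says the sample size was set for those analyses. Nor does the plan claim to show non-inferiority on both outcomes in both powered skin types at once, so power for that combined event is not a fair test.

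The low-correlation figures run against the plan's own expectation, so 0.9 to 0.95 is the fairer range. The skin-type strata could also end up larger. If 1050 are randomised, about 80 are type V/VI, and the other two strata are not capped at 350, each has about (1050 − 80)/4 ≈ 242 per arm. Joint power would then be 83% at r = 0 and 88% at r = 0.9. However, section 3.1 lists 350 for each of those strata, so this cannot be relied on.

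Finally, splitting alpha would also hold 2.5% if one success is to be enough. At 1.25% each, power to win at least one outcome in a skin type is 80.1% at r = 0.8 and 77.5% at r = 0.9. That is a legitimate alternative, but it fits the co-primary label less well and section 8.3 rejects an adjustment.

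**Conclusion.** The point holds as a gap in the success rule together with a flawed reason for leaving alpha unadjusted. The documents lean towards requiring both outcomes but never make that the decision rule, and the correlation argument belongs to the opposite rule. If one success is enough, the overall one-sided error is 3.2% to 3.5% at correlations of 0.95 to 0.9, and up to 4.9% at 0, with both outcomes exactly at the margin. If both are required, error is controlled, and joint power in a skin type at 175 per arm is about 75% to 77% over the same correlations (64% at 0) against 80% per outcome. These figures rest on the plan's 50% response rates, a normal approximation and an assumed correlation.

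This should be fixed before unblinding. It does not invalidate the sample size for the pooled primary analysis.

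**What to change.** In section 8.1, state before unblinding that an overall conclusion of non-inferiority, pooled or in a skin type, requires both PGA and DLQI to meet the margin, each at one-sided 2.5% without adjustment. State also that each outcome's result will be reported separately whatever the overall conclusion.

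In section 8.3, replace the correlation argument with this rule. Label the 80% as power per outcome. Add the joint power over a stated correlation range: for example, about 64% at 0 and 75% to 77% at 0.9 to 0.95 in a skin type with 175 per arm, and 97% or more pooled.

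The cost is a change of wording and a less favourable stated power in the skin types. No extra patients are needed. Restoring 80% joint power in a skin type would take about 190 to 196 per arm at correlations of 0.95 to 0.9, but that is not needed to resolve this point.

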8.4 Statistical Methods

8.4.1 Baseline Data

Our initial analyses will utilize descriptive statistics to detail the characteristics of the study cohort. Continuous variables will be described with means and standard deviations. Categorical variables will be summarized using counts and proportions. Summary statistics will be generated for the full study cohort as well as stratified by treatment arm, skin type, and the combination of treatment arm and skin type. Imbalance in covariates between the home and office based phototherapy arms will be described by calculating the differences in means or proportions between the two arms with 95% confidence intervals.

8.4.2 Efficacy Analysis

The primary efficacy endpoint is both physician reported (the physician global assessment) and patient reported (DLQI) The efficacy analysis approach is detailed in section 8.1 and 8.2.

8.4.3 Safety Analysis

The primary safety outcome is the proportion of patients reporting treatment-emergent adverse events. Adverse events include patient reported burns and their severity. We hypothesize that safety of home based UVB phototherapy will not be different from office based phototherapy. We anticipate based on extensive experience, that the number of clinically significant burns (i.e., which may require the patient to seek advice from the treating physician and occur due to human error) will be rare (affecting <1% of patients) and typically can be managed at home with over the counter remedies.

As ultraviolet light does not have adverse effects beyond the skin, our stakeholders believe that safety assessments should focus on skin related events such as burns and serious adverse events. We will summarize the number, severity, and type of adverse events experienced by patients in each treatment arm. We will compute the proportion of patients experiencing adverse events by treatment arm, with 95% CI. Similar to analyses for our effectiveness outcomes, we will also fit skin type-adjusted logistic regression models and use standardization to estimate adjusted risk differences between treatment arms. In addition to pooled safety analyses, we will also compare the proportion of patients experiencing adverse events between office-based and home-based phototherapy arms within each skin type sub-group

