3.2.3 Primary Safety Endpoints

The primary safety outcome is the proportion of patients reporting treatment-emergent adverse events. Adverse events include patient reported burns and their severity. Patients will be queried about these events immediately prior to each phototherapy treatment by the clinical staff (for patients assigned to office base phototherapy) or by the home phototherapy machine. We will also evaluate all serious adverse events regardless of their relationship to treatment. All patients will be queried about SAEs by the sites at the visit 2. Patients can spontaneously report SAEs at any point during the study.

4 Study Population and Duration of Participation

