4.2 Exclusion Criteria

Exclusion criteria:

- 1. Patients who are judged unable or unwilling to comply with either in office or in home phototherapy due to time, work, school, or other financial constraints
- 2. Patients judged unable to follow home phototherapy protocol due to failure to demonstrate understanding of the following:
 - a. How to operate the phototherapy device
 - b. How to follow the dosing protocol
 - c. Requirement to wear protective eyewear and genital protection equipment
- 3. Patients with known history of lack of efficacy to phototherapy or treated with phototherapy 14 days prior to baseline visit.
- 4. Psoriasis predominantly located on scalp, body folds, genitals, palms and/or soles or with a physician global assessment average of ≤ 1.0
- 5. Patients deemed unsafe to be treated with phototherapy:
 - a. History of photosensitivity or autoimmune disease such as lupus or dermatomyositis which can be aggravated by ultraviolet radiation
 - b. History of arsenic intake
 - c. Unable to tolerate standing for required duration of treatment due to age or physical function
 - d. History of melanoma or multiple non-melanoma skin cancers that in the opinion of the principal investigator contraindicates treatment with phototherapy
- 6. Clinical site deems the participant is ineligible for reason other than eligibility or screening criteria.

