5.4 Storage

The home phototherapy device should be used in a private area of the home and must be near electrical service and in a place free from temperature and environmental extremes. There are no sterilization requirements for the device. The patient must wear protective eyewear during the treatment and ensure that other family members or pets are not exposed to incidental ultraviolet radiation from the device.

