6.2.2 Weeks 2,3,5,6,7,9,10,11

- Administer NB-UVB phototherapy three times per week
- Patient reported response to phototherapy prior to treatments. For those on office treatment, data is entered by the sites. For those on home treatment, data is recorded on the home device.
- Phototherapy session number and dose. For those on office treatment, data is entered by the sites. For those on home treatment, data is recorded on the home device.

6.2.3 Weeks 4 & 8

- Administer NB-UVB phototherapy three times per week
- Patient reported response to phototherapy prior to treatments. For those on office treatment, data is entered by the sites. For those on home treatment, data is recorded on the home device.
- Phototherapy session number and dose. For those on office treatment, data is entered by the sites. For those on home treatment, data is recorded on the home device.
- Patient reported DLQI
- Patient reported target lesion image
- Patient reported psoriasis topical treatment

6.2.4 Week 12

- Administer NB-UVB phototherapy three times per week
- Patient reported response to phototherapy prior to treatments. For those on office treatment, data is entered by the sites. For those on home treatment, data is recorded on the home device.
- Phototherapy session number and dose. For those on office treatment, data is entered by the sites. For those on home treatment, data is recorded on the home device.
- Site reported concomitant oral and biologic psoriasis medications

6.2.5 End of Treatment/ Visit 2 (occurs at Week 12 (plus or minus 2 weeks) or at time that patient discontinues phototherapy, whichever comes first)

- Clinician measured PGA score
- Clinician measured BSA assessment
- Patient reported DLQI
- Patient reported time spent on travel, cost of travel, and time spent on phototherapy (administered by site)
- Patient reported target lesion image
- Site reported concomitant oral and biologic psoriasis medications
- SAE Assessment

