6.5.1 Data Collection and Follow-up for Withdrawn or Early Termination Participants

Participants who withdraw consent to participate in the study will be asked to report the reason for withdrawal.

7 Study Evaluations and Measurements

The data collected in this study are all considered relevant for routine clinical care. In routine clinical care, there is some variation in which assessments are conducted and thus we will standardize assessments for the purpose of the study.

Investigator reported measures:

1. Physicians Global assessment (PGA): This is a three item measure that asks the physician or his or her designee to assess the thickness, redness, and scale of psoriasis plaques.

2. Body Surface Area (BSA): This is a measure that asks the physician or his or her designee to assess the body surface area affected by psoriasis using the handprint method in which the palm of the entire hand approximates 1% of the body surface area. To do this, the patient's handprint, including the entire area of the palm and all 5 digits with the fingers close together but not overlapping, is used as a guide to estimate 1% of the BSA

3. Number of phototherapy treatments and dose received: This data is routinely collected in clinical practice. It will be reported by the sites for patients receiving office treatment and will be obtained from the machines for those receiving home based treatment

- 4. Copay for office-based phototherapy
- 5. Concomitant treatment

Patient reported measures:

1. Dermatology Life Quality Index: (DLQI): DLQI is a 10 item survey that asks patients questions about their health related quality of life on a 0-3 scale. DLQI is routinely used in clinical trials of psoriasis treatments and can also be used routinely in clinical practice.

2. Patient reported response to phototherapy: This is a standard question asked to the patient to document the degree and duration of erythema induced by the prior phototherapy treatment session. It is standard of care.

- 3. Patient reported time spent on travel, cost of travel, and time spent on phototherapy
- 4. Patient reported concomitant psoriasis topical treatment

5. Photograph of target psoriasis lesion (at a subset of study sites)

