7.6 Safety Evaluations

Safety will be monitored by the local clinicians.

Patients will be queried about the reaction to phototherapy (i.e., burns) immediately prior to each phototherapy treatment as is standard practice. Patients will contact the study clinicians for any significant reaction to phototherapy (a burn which requires medical attention such as one associated with significant pain that interrupts usual activities or skin blistering). Patients will be queried about SAE's at visit 2. Patients can spontaneously report SAEs at any point during the study.

8 Statistical Plan

8.1 **Primary Endpoint**

Primary analyses will be based on the intent to treat (ITT) population defined as all patients meeting eligibility requirements who are randomized to one of the two study arms. In the ITT population, we will compare the two treatment arms with respect to two primary effectiveness outcomes. The first primary effectiveness outcome is treatment response, a dichotomous indicator of whether a patient has achieved clear/almost clear skin (score of 0 or 1), based on the Physician's Global Assessment (PGA) at the earlier of week 12 (visit 2), defined as the twelfth week after the start of treatment, or the time of discontinuation of phototherapy. In our primary analyses, patients who drop out of the study prior to achieving clear/almost clear skin or week 12, whichever comes first, will be classified as treatment failures (i.e., failure to achieve clear/almost clear skin). The second primary outcome is the patient-reported Dermatology Life Quality Index (DLQI) assessed at week 12. We will dichotomize DLQI at a score of 0-5 (corresponding to no to small impact on quality of life) versus a score >5. Patients failing to complete the week 12 DLQI assessment will be assumed to have DLQI >5 and therefore classified as a non-responder on this measure.

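### The safety rationale in 8.4.3 says UV has no effects beyond the skin, at odds with the plan's mandatory eyewear, and it is unclear whether patients are asked about non-serious eye symptoms

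*Combined protocol and SAP*

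**What the plan says.** **Scope.** Section 8.4.3 reasons: "As ultraviolet light does not have adverse effects beyond the skin, our stakeholders believe that safety assessments should focus on skin related events". It adds serious adverse events (SAEs), hypothesises no safety difference between home and office, and plans a summary of events by number, severity and type in each arm. Safety (tolerability) is part of the primary objective (2.1).

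**Eye protection.** Section 5.4, on the home device, says: "The patient must wear protective eyewear during the treatment". Section 4.2 excludes patients who do not demonstrate understanding of several points, one of which is: "Requirement to wear protective eyewear and genital protection equipment".

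**What is asked.** Section 7 describes the per-session question as one to "document the degree and duration of erythema induced by the prior phototherapy treatment session". Section 7.6 says: "Patients will be queried about the reaction to phototherapy (i.e., burns) immediately prior to each phototherapy treatment as is standard practice". It also defines the reaction for which a patient should contact the clinic as a burn needing medical attention. Other sections are wider. In 3.2.3 the outcome is treatment-emergent adverse events, with burns given as included, and the query is made "immediately prior to each phototherapy treatment by the clinical staff (for patients assigned to office base phototherapy) or by the home phototherapy machine". Section 9.2 has the care provider record reported adverse events before each treatment, with no limit to skin. The safety item at Visit 2 (6.2.5) is "SAE Assessment".

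**What can be recorded.** Any adverse event related to phototherapy (9.1.1), including events abstracted from the chart or the home device (9.2). A serious eye injury could qualify as an SAE through the important-medical-event criterion (9.1.2). The phototherapy response form is listed as 16.5.4, but its content is not in the text reviewed.

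**The concern.** The premise in 8.4.3 is unqualified, and it is used to decide where safety assessment should look. A plan that requires eye protection, and screens out patients who do not grasp the need for it, already treats the eye as a site to be protected. The two positions do not fit together.

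This would be only a matter of wording if eye symptoms were clearly asked about. They may not be: the two sections that describe the content of the per-session question both confine it to skin. If the form follows them, a patient with sore or watering eyes after a session has to volunteer it. The by-type table in 8.4.3 could then show few or no eye events, and a reader could not tell whether few occurred or few were asked about. Symptoms that were never solicited cannot be recovered at analysis.

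The trial is meant to inform a decision on home treatment, where the patient applies the precaution without staff present, so an uninterpretable row in that table is a real, if small, loss.

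**Working it through.** The plan states no eye-event rate, so there is no figure of its own to reproduce. The main check is a reading of the sections against one another.

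1. *Rationale against rules.* 8.4.3: no effects beyond the skin. 5.4 and 4.2: eyewear required, and understanding of it a condition of entry. These are inconsistent as rationale. No operating rule contradicts another.

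2. *Routes for a non-serious eye symptom.*
   - Per-session question: covered if 3.2.3 is read broadly; not covered on the descriptions in sections 7 and 7.6; unresolved without form 16.5.4.
   - Per-session recording by the care provider (9.2): open to any event type, but only for events that are reported.
   - Visit 2 query: serious events only.
   - Chart abstraction (9.2): only if the symptom reached the chart.

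3. *Arms.* Office patients are asked by staff and home patients by the device (3.2.3). Staff may hear symptoms that nobody asked about, and the documents do not say whether the device accepts any. Ascertainment could differ, but nothing in the documents gives a direction or size.

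**Illustration only.** The figures below show what a zero count could mean. They do not measure under-ascertainment.

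- Arm sizes: 1050/2 = 525 (4.5), or (350 + 350 + 80)/2 = 390 using the skin-type numbers in 3.1.
- Exact two-sided 95% upper limit with 0 events = 1 − 0.025^(1/n). This gives 0.94% for n = 390 and 0.70% for n = 525. The limit applies to the true rate only if all n patients were asked; otherwise it bounds the recorded rate.
- Patients needed for that limit to fall below 1%: ln(0.025)/ln(0.99) = 367.04, so 368 per arm, which is 94.4% of 390 or 70.1% of 525. The 1% is borrowed from the plan's expectation for clinically significant burns (8.4.3) and is not an eye-event rate.
- Assume a true rate of 1% and n = 525. With full capture, 525 × 0.01 = 5.25 events are expected, and the chance of recording none is 0.99^525 = 0.5%. With 20% capture, 1.05 are expected and the chance of none is 0.998^525 = 35%. Over assumed true rates of 0.2% to 2%, expected recorded events run from 1.05 to 10.5 with full capture and from 0.21 to 2.1 with 20% capture. Both the rates and the capture proportions are assumptions.
- Between arms, 0 against 0 gives a Newcombe 95% interval of about ±0.98 percentage points (390 per arm) or ±0.73 (525). Even full ascertainment would leave the comparison descriptive.

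**The case against.** The strongest reply is that the plan is wider than 8.4.3 suggests. Burns are named in 3.2.3 as included, not as the whole outcome; 9.2 has adverse events recorded before each session; and 9.3 has the site review all of them. The instrument that would settle the question, form 16.5.4, is not shown, and a form that is not shown is not a form without an eye item. This stands. It rules out saying that no query covers eye symptoms. It does not remove the narrower descriptions in sections 7 and 7.6, which is why the text is best called mixed.

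A second reply is that eyewear is a precaution: a plan may require it and then expect no eye events in protected patients. That is a defensible position, but it is not what 8.4.3 says. Its claim is about ultraviolet light itself, not about treatment with the eyes covered.

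A third is that limited event collection is a deliberate choice, made with stakeholders, for a pragmatic trial of two standard treatments. This also stands, and it is why the change should be confined to one item. A recall question at Visit 2 has weaknesses of its own, set out with the fix.

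**Conclusion.** The point holds as a cheap improvement. The premise in 8.4.3 is inconsistent with 5.4 and 4.2. On the visible text, non-serious eye symptoms appear to depend on spontaneous report or chart abstraction, by routes that differ between arms. This rests on sections 7 and 7.6 describing the per-session form accurately, which cannot be confirmed. If form 16.5.4 already has an eye item in both arms, only the wording point remains.

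The size of any under-ascertainment cannot be computed, because the documents give neither an event rate nor a capture rate. Efficacy, sample size and the burn comparison are unaffected.

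Three stronger readings are not supported:

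- A reader might infer that eye events are left out of the safety data. They are recordable under 9.1.1 and 9.2, and serious ones fall under the SAE query.
- A reader might infer that home treatment will look safer than it is. The routes differ by arm, but the documents show no direction.
- A reader might infer that eyewear is the only precaution outside the patient's own skin that is left to the home patient. The same sentence of 5.4 also asks the patient to keep family members and pets from being exposed.

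**What to change.** 1. Qualify the sentence in 8.4.3, for example: adverse effects are expected mainly in the skin and, where eyewear is not worn, possibly in the eye.
2. Check form 16.5.4. If it has no eye-symptom item in both arms, add one, in identical words for both arms, to the patient questions that the site already administers at Visit 2 (6.2.5). This gives both arms the same route, which the per-session query does not.
3. Report eye events as a named type by arm, descriptively, with the number of patients asked. Keep them apart from the burn comparison, since burns are asked about before every session and this item would be asked once.

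The cost is one sentence, at most one question at an existing visit, and one table row, with no extra staff or procedure. The downsides are recall over about 12 weeks, no capture in patients who miss Visit 2, and some non-specific complaints that would need the site review already provided for in 9.3. Rewording the sentence alone would make the document consistent but would change no result.
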